Among the drugs that have been tested in clinical trials in patients with TBI are corticosteroids. Based on the results of the MRC CRASH study (9), the current Clinical Practice Guidelines (10) do not recommend the administration of high doses of methylprednisolone to improve the prognosis for patients with TBI. However, due to the experience of dexamethasone in patients with brain tumors, this glucocorticoid is still used in neurosurgical patients with various pathologies and its role is currently being reassessed in patients with TBI and chronic subdural hematomas (11,12).

In daily clinical practice, patients with TBI and cerebral contusions developing an area of pericontusional edema are among the patients who are occasionally given dexamethasone on the belief that this edema is similar to that of tumors. Clinically, the beneficial effect of dexamethasone in patients with tumors and peritumoral edema, which is primarily vasogenic, has been well demonstrated (13).

Cerebral edema is classified as cytotoxic and vasogenic. Cytotoxic edema is primarily intracellular and appears after ischemic insults. In vasogenic edema, however, water has an extracellular location and appears when there is a disruption or an abnormal increase in the permeability of the blood brain barrier (14). Published studies have described the presence of a mixed component (vasogenic and cytotoxic) in patients with TBI and cerebral contusions (15,16). Experimental studies have shown that the alteration of the blood brain barrier is biphasic. There is a rapid initial opening phase after the trauma that occurs in the first hours. Subsequently, a second opening phase of the blood brain barrier occurs, which usually begins between 3-7 days after the trauma (17). At the clinical level it has been proven that can take days or weeks for the blood brain barrier to return back to normal (17,18). For this reason it is possible that there is a therapeutic window for corticosteroids in this type of patients. However, it is well known that corticosteroids have a beneficial effect on vasogenic edema (as in patients with tumors) but none on cytotoxic edema.

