The design will allow us to find out how effective the treatment actually is in routine everyday practice. Ethically, this randomized controlled trial can only be undertaken if there is collective scientific uncertainty about which of the interventions being compared is more likely to benefit patients. However, for an individual clinician to be able to recommend enrolment of a patient into a trial, they must be substantially uncertain about the appropriateness of the trial treatment in that particular patient. The eligibility criteria for the DEXCON trial are based on this uncertainty principle. A patient can be enrolled only if the responsible clinician is substantially uncertain as to which of the trial treatments would be most appropriate for that particular patient. Using the uncertainty principle should allow the process of this trial to be closer to what is customary in normal medical practice.

Eligible patients

Adults with TBI who fulfill the following inclusion criteria are eligible:

- Patients who have suffered a head injury and have one or more cerebral contusions with visible pericontusional edema in the CT scan.
- Patients with brain contusions in whom non-surgical treatment has been selected initially.
- Age 18 or over and under 85
- Signing of informed consent by the patient or by his legal representative.

The fundamental eligibility criterion is the responsible clinician's 'uncertainty' as to whether or not to use dexamethasone in a particular patient with TBI. This pragmatic approach will allow us to see whether the intervention improves patient outcomes under real-life conditions.

The exclusion criteria are the following:

- Patients with TBI and brain contusions who have required surgery to evacuate the cerebral contusion before randomization.
- Patients with TBI who have required a craniotomy before randomization for any other reason: evacuation of subdural, epidural hematoma or depressed skull fracture.
- Patients with an extracranial Injury Severity Score greater than 18 points.
- Patients in whom the use of corticosteroids is contraindicated.
- Patients who take oral corticosteroids chronically.
- Patients included in another clinical trial.
- Known intolerance or hypersensitivity to dexamethasone.
- Patients with allergy or intolerance to the following excipients contained in dexamethasone / placebo capsules: lactose, corn starch or microcrystalline cellulose.
- Patients with a history of psychotic disorders.

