- Patients with inability to take medication orally due to swallowing problems in which it is not indicated to place a nasogastric tube.
- Pregnant or breastfeeding patients.
- Patients in a GCS 3 points situation with bilateral dilated pupils.
- Patients with associated spinal cord injuries.
- Patient with any systemic condition that contraindicates the use of corticosteroids.

Randomization

To ensure a balanced sample size across groups over time, the statistician of the study will apply the block randomisation method with a block size of 2 (two possible sequences: AB and BA) and will be generated with the statistical package R, version 3.5.3, a list for each hospital. A limited number of treatments will be available in each

hospital, sent from the Pharmacy Department of Son Espases Hospital, which will be numbered, and will be assigned in a correlative manner.

Patients, clinical staff, evaluators of the results as well as the statistical team will be blinded to the assignment of medications.

Only the pharmacist, who masks the capsules and labels the containers, will know the assignment of the codes, and will keep them blind until the last phase of the study, after the main statistical analysis, or when unmasking is required.

Once it is verified that the patient meets all the inclusion criteria and none of the exclusion criteria, and after signing the informed consent by the patient himself or by the closest relative, the doctor responsible for the patient will correlative assign the number to the patient.

Settings

Initially, the study will be carried out in Son Espases Hospital (Palma de Mallorca) and 12 de Octubre Hospital (Madrid). During the first year, all possible patients will be tried to be recruited. A minimum of 60 patients are expected between the two hospitals.

If after the first year interim analysis the Trial Steering Committee (TSC) decides to continue the trial, recruitment will begin in the hospitals included in the Spanish National Registry of Traumatic patients in the ICU (RETRAUCI Network) which includes 56 public hospitals.

Outcome measures

After a patient has been randomized, the outcome will be collected even if the trial treatment is interrupted or is not actually given

Primary outcome

The primary outcome is the functional status (outcome) of TBI patients one and six months after the trauma according to the Glasgow Scale Outcome Extended (GOSE).

Secondary outcomes (Supplemental data)

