-Number of episodes of neurological deterioration in both groups of patients during the 12 days of treatment.

- Symptoms associated with TBI in both groups of patients during the 12 days of treatment.
- Volume of pericontusional edema before and after 12 days of treatment in both groups of patients.
- Presence of adverse events between the two groups during the 12 days of treatment.
- Neuropsychological tests between the two groups of patients one month and 6 months after the TBI.

Estimated event rate

In our previous studies we have described that among TBI patients with brain contusions not treated with dexamethasone, the proportion of patients with good recovery (GOSE 7 and 8) was 50%.

Sample size and treatment effect size that should be detectable

Since the data available in this type of patients with this treatment is scarce and inconclusive, we will perform a randomized, triple-blind, placebo controlled trial with an interim futility analysis (interim analysis). The primary endpoint for the DEXCON TBI trial is the good recovery (GOSE 7-8) one month after the TBI.

A study with 600 patients would have about 80% power (two sided alpha=5%) to detect a 12% absolute increased (from 50% to 62%) in good recovery (GOSE 7-8). It includes an inflation of 10% due to non-adherence (withdrawal of consent, loss to follow-up, cross-over or change of treatment).

Recruitment of collaborating investigators

The trial will recruit hospitals from Spain. Suitable collaborating hospitals and investigators will be assessed in terms of the trauma service that they provide and their ability to conduct the trial.

Before the trial can begin at any site, the local Principal Investigator must agree to adhere to Good Clinical Practice Guidelines and all relevant national regulations. In addition, all relevant regulatory and ethics approvals should be in place before the trial starts at a site.

Ethical considerations, information giving and written informed consent

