Dexamethasone doses are those commonly used in neurooncology and there is an extensive experience in its use. It will be a short and descending course: 4mg/6 hours (2 days); 4 mg/8 hours (2 days); 2 mg/6 hours (2 days); 2 mg/8 hours (2 days); 1 mg/8 hours (2 days); 1 mg/12 hours (2 days).

Drug manufacture, blinding and supply of trial treatment

Dexamethasone (Forteocortin®) will be acquired from ERN, SA. Laboratories (Barcelona, Spain). The Son Espases Pharmacy Department will be in charge of developing and conditioning the 4mg, 2mg and 1mg dexamethasone / placebo capsules needed for 12 days of treatment, keeping the researchers blind.

The preparation and conditioning of the capsules will be carried out following the standardized work procedures of the pharmaceutical laboratory and its quality controls, previously authorized by the Agencia Española del Medicamento (AEMPS).

The Son Espases Pharmacy Department will be responsible for identifying the containers and sending them by courier to the participating hospitals. A record of the dispensing of test samples will be kept and will be sent in acknowledgment of receipt for control.

Patients, clinical staff, evaluators of the results as well as the statistical team that will perform the analysis will not know the assigned treatment. A randomization list will be created for each hospital. The randomization sequence will only be known by the Pharmacy Department of Son Espases Hospital.

Administration of trial treatment

Each patient will receive 3 containers with the correspondingly identified doses, and an information sheet explaining dose and frequency for proper oral administration.

Other treatments for traumatic brain injury

There is a wide spectrum of treatments for TBI. As the trial will be conducted in Spain, each participating site should follow its own clinical guidelines for the treatment of TBI patients. There is no need to withhold any clinically indicated treatment in this trial.

Dexamethasone or placebo would be provided as an additional treatment to the usual management of TBI.

Safety and Adverse events

Dexamethasone has a well documented safety profile. Nevertheless, data on adverse events, such as infectious complications, hyperglycemia, gastro intestinal bleeding or appearance of psychotic symptoms will be collected as secondary outcomes and will be presented to the independent Data Monitoring Committee (DMC) for blinded review.

Definitions

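### Chronic oral use is the only exclusion on prior steroid exposure, so patients already given a systemic corticosteroid for this injury can enter either arm and dilute the comparison

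*Combined protocol and SAP*

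**What the plan says.** The exclusion list under Eligible patients has four lines on corticosteroids in general or dexamethasone in particular, apart from the one on capsule excipients. Three concern whether the patient can safely take the drug: "Patients in whom the use of corticosteroids is contraindicated", "Known intolerance or hypersensitivity to dexamethasone" and "Patient with any systemic condition that contraindicates the use of corticosteroids". One concerns exposure: "Patients who take oral corticosteroids chronically". The same list bars patients who had surgery for the contusion, or a craniotomy for another reason, before randomisation. Earlier treatment of the injury was thus considered, but earlier use of the trial drug is not mentioned.

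Four other places bear on the point:

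- Background: patients with contusions and pericontusional edema "are among the patients who are occasionally given dexamethasone on the belief that this edema is similar to that of tumors".
- Eligible patients: "The fundamental eligibility criterion is the responsible clinician's 'uncertainty' as to whether or not to use dexamethasone in a particular patient with TBI".
- Other treatments for traumatic brain injury: "There is no need to withhold any clinically indicated treatment in this trial".
- Estimated event rate: "among TBI patients with brain contusions not treated with dexamethasone, the proportion of patients with good recovery (GOSE 7 and 8) was 50" per cent.

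**The concern.** The trial is meant to compare a course of dexamethasone with none. The protocol says that the drug is sometimes given to this kind of patient in ordinary practice, yet an acute course started for the injury meets no exclusion: it is not chronic, and it may not be oral. If such a patient is allocated placebo, the placebo arm contains some active exposure. If allocated dexamethasone, the patient receives a repeated or overlapping course.

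In either case the contrast for that patient is smaller than the one planned. The efficacy difference shrinks, as do the differences in steroid-related events that the trial sets out to measure (hyperglycemia, infection, gastrointestinal bleeding, psychotic symptoms). The planning control rate was observed in untreated patients, so admitting treated ones departs from the sample-size assumption.

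Nothing in the analysis plan would reveal or correct this. The adjustment covariates are age, pupil reactivity, blood pressure and GCS. The modified intention-to-treat rule removes patients for withdrawn consent, loss to follow-up or an incomplete course, not for earlier exposure.

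**Working it through.** **Inputs from the protocol** (Randomization; Estimated event rate; Sample size and treatment effect size): control rate 50%, dexamethasone rate 62%, two-sided alpha 5%, power about 80%, 600 patients, 10% inflation for non-adherence, 1:1 allocation.

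**Inputs assumed, because the documents give none:** the share f of patients who had a corticosteroid for this injury before randomisation (2% to 20%), and the fraction e of the 12-point benefit that this exposure gives a placebo patient (one half or all of it). Pre-treated patients in the dexamethasone arm are taken to gain nothing extra.

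**1. Reproduce the stated sample size.** For two proportions with pooled variance under the null and no continuity correction:

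n per arm = [1.96 × √(2 × 0.56 × 0.44) + 0.842 × √(0.50 × 0.50 + 0.62 × 0.38)]² / 0.12² = 267.4, rounded up to 268.

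Total 536; 536 / 0.90 = 596, which agrees with the stated 600. Conversely, 600 × 0.90 = 540 evaluable, or 270 per arm, gives power of 80.4%. There is no sample-size error here.

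**2. Dilute the contrast.** Placebo rate = 0.50 + 0.12 × f × e; the dexamethasone rate stays at 0.62. For f = 10% and e = 1, the placebo rate is 0.50 + 0.012 = 0.512 and the difference is 10.8 points. Power with 270 per arm is

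Φ{[0.108 × √270 − 1.96 × √(2 × 0.566 × 0.434)] / √(0.512 × 0.488 + 0.62 × 0.38)} = Φ(0.575) = 71.7%.

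**3. Results over the assumed range.** The last column is the total needed to restore 80% power, including the 10% inflation.

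| Pre-treated share f | Benefit carried over e | Difference (points) | Power, 270 per arm | Total for 80% power |
|---|---|---|---|---|
| 0% | none | 12.0 | 80.4% | 596 |
| 2% | half | 11.88 | 79.6% | 607 |
| 2% | full | 11.76 | 78.8% | 620 |
| 5% | half | 11.7 | 78.4% | 627 |
| 5% | full | 11.4 | 76.3% | 658 |
| 10% | half | 11.4 | 76.3% | 658 |
| 10% | full | 10.8 | 71.7% | 734 |
| 20% | half | 10.8 | 71.7% | 734 |
| 20% | full | 9.6 | 61.6% | 925 |

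**4. Does the 10% inflation already cover this?** It names withdrawal, loss to follow-up and departures from the allocated treatment. Exposure before entry is not among them. The whole 10% is used in going from 600 to 540, which is what yields 80.4% before any dilution. Dilution also acts on the difference itself, so the number needed rises roughly with the inverse square of what remains: 1 / 0.9² = 1.23 for the 10%, full-benefit row, against 734 / 596 = 1.23 in the table.

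**The case against.** The strongest reply is the uncertainty principle. A patient may enter only if the responsible clinician is substantially uncertain about dexamethasone, and a clinician who has already prescribed it will usually not be. This closes much of the route. It does not close all of it, because the criterion asks for the present clinician's view and is silent on what another team has already given.

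Four stronger readings are tempting, and the documents do not support them.

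- *Chronic oral use is the only steroid exclusion.* It is not; three further lines cover contraindication and intolerance. It is the only line on prior exposure.
- *The comparison is biased in favour of one arm.* Exposure before randomisation is a baseline characteristic and should balance under 1:1 allocation within each hospital. The randomised contrast remains valid for those enrolled. The same holds for baseline edema volume and the 10 mL subgroup: the inclusion CT, taken in the 24 hours before randomisation, could follow a steroid dose, but it would do so in both arms.
- *The protocol permits open-label dexamethasone beside the capsules.* The sentence on not withholding treatment is about other treatments for TBI. It is ambiguous about corticosteroid; it does not grant permission. Open-label use after entry would also fall at least partly under the departures named in the 10% inflation.
- *Entry is open-ended, so transfers of pre-treated patients are to be expected.* The readable text states no maximum time from injury to randomisation, but the trial-overview figure is not available, and no transfer pathway is described.

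It is also fair to say that the full-benefit rows are a worst case, and that the Background's word for the frequency of use does not establish 10% or 20%. The case report form is not among the documents, so it may already capture non-trial corticosteroid.

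**Conclusion.** The gap holds as a point about eligibility. As written, a patient already given a systemic corticosteroid for the index injury can be randomised, in a population that the protocol itself says occasionally receives one, and against a planning rate from patients who did not. The consequence is dilution of the efficacy and steroid-safety contrasts toward no difference, with some loss of power.

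The loss from the planned 80.4% is about 2 to 4 percentage points if 5% of patients are pre-treated, and about 4 to 9 if 10% are. At 2% it is under 2 points. All of this rests on assumed exposure rates, on half to full benefit carried over, and on no added benefit in pre-treated patients allocated dexamethasone. The documents do not allow the true size to be fixed. The point is worth acting on because the correction is cheap, not because the loss is known to be large.

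**What to change.** 1. Under Eligible patients, extend the exclusion on chronic oral use so that it also covers any patient who has received a systemic corticosteroid, by any route, for the index injury between the injury and randomisation. Limiting it to the index injury avoids losing patients over a dose given for an unrelated reason.
2. Record non-trial corticosteroid on the case report form, with drug, route and dates, both before and after randomisation, if the form does not already do so.
3. Reconcile the sentence on not withholding treatment, under Other treatments for traumatic brain injury, with the placebo comparison, so that sites know how non-trial corticosteroid relates to the trial. The clinical rule itself is for the investigators to set.

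If the investigators prefer to admit pre-treated patients on pragmatic grounds, the protocol should say so, and a sensitivity analysis without them should be pre-specified.

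The cost is one reworded criterion, a small addition to the case report form, and the loss of the occasional pre-treated patient. The sample size need not change.

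### Fixed blocks of two per hospital, printed in the protocol, tie each patient's arm to a partner's: a conditional weakness that larger, undisclosed, varying blocks would roughly halve

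*Combined protocol and SAP*

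**What the plan says.** The Randomization section gives balance as the purpose: "To ensure a balanced sample size across groups over time". The method is a "block randomisation method with a block size of 2 (two possible sequences: AB and BA", with a separate list for each hospital; the section on drug manufacture, blinding and supply repeats that there is one list per hospital. Packs come from the coordinating hospital's pharmacy, "which will be numbered, and will be assigned in a correlative manner". At enrolment "the doctor responsible for the patient will correlative assign the number to the patient".

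Several protections are stated. The same section says "Patients, clinical staff, evaluators of the results as well as the statistical team will be blinded to the assignment of medications" and "Only the pharmacist, who masks the capsules and labels the containers, will know the assignment of the codes". The Treatment section provides a matching placebo. The Unblinding section expects unblinding to be rare, but when it happens the caller is told the arm.

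Neither a varying block size nor concealment of the block size from sites is described. Under Collaborators' responsibilities, each local principal investigator undertakes to follow this protocol, so the block size is available to sites.

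**The concern.** With a known block of two, the second allocation of each pair is the mirror image of the first. The consequence depends on when the first arm becomes known or suspected.

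- **Before the partner is enrolled:** the next allocation is foreseeable, and the choice of whom to enrol can be influenced. Blinded outcome assessment cannot undo selection at entry. The eligibility section rests entry on the responsible clinician's own uncertainty, which leaves room for this.
- **After the partner is enrolled:** allocation concealment for that patient is unaffected, but the arm can be deduced by site staff who know the block size and the pack order.

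The protocol contains one certain route to an arm (emergency unblinding) and one possible route: Supplemental Data 1 has peak capillary glucose and insulin need recorded daily in a corticosteroid trial.

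**Working it through.** **Inputs from the protocol.** Block size 2, one list per hospital, consecutive use of packs (Randomization). 600 patients, 50% versus 62% good recovery, two-sided 5%, about 80% power, 10% inflation (sample size section). First-year recruitment: "A minimum of 60 patients are expected between the two hospitals" (Settings), or about 100 (Interim analysis).

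**Plan's own figure.** The protocol gives no predictability figure. Its sample size does reproduce: the pooled two-proportion formula gives 268 per arm, 536 in total, and 536/0.9 = 596, close to 600. I use 300 per arm, and 270 (600 × 0.9 / 2) as a check.

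**1. The link between partners.** In a block of size b with known boundaries, another member is in the opposite arm with probability p = (b/2)/(b−1). A guess of accuracy a about one patient gives the other with accuracy a·p + (1−a)(1−p).

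- b = 2: p = 1, so the accuracy is a itself: 0.60 → 0.60, 0.80 → 0.80, 1.00 → 1.00.
- b = 4: p = 0.667, so 0.80 → 0.60.
- b = 6: p = 0.600, so 0.80 → 0.56.
- At a = 0.50 the result is 0.50 for every block size, so the weakness is conditional.

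**2. Unblinding.** Under block 2, one revealed arm fixes the partner's. With undisclosed 4/6 blocks the next patient is in the opposite arm with probability 3/4 × 2/3 + 1/4 × 1/2 = 0.625 (block 4) or 5/6 × 3/5 + 1/6 × 1/2 = 0.583 (block 6). The length-weighted value is (4 × 0.625 + 6 × 0.583)/10 = 0.60.

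**3. Timing.** Assuming an equal split between the two hospitals and uniform Poisson accrual, the mean gap between consecutive patients at a hospital is 365/30 = 12.2 days (60 patients) or 365/50 = 7.3 days (100 patients). The second of a pair arrives at least 3 days after the first with probability exp(−3/12.2) = 0.78 or exp(−3/7.3) = 0.66. Timing alone does not rule out some observation of the first patient.

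**4. Illustrative bias (behaviour assumed, not from the documents).** Half of the predictable patients are acted on, and prognosis is steered by 10 points. Under block 2 the predictable patients are the second of each pair, so a quarter of all patients are acted on. With guess accuracy g,

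bias = 0.5 × 0.5 × (2g−1) × k × 0.10,

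where k = 1 if steering goes in one direction only, and k = 2 if every clinician steers up or down according to the predicted arm. Type I error = Φ(−1.96 − bias/se) + 1 − Φ(1.96 − bias/se), with se = √(2 × 0.25/n) = 0.0408 at n = 300.

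| g | One-way bias, points | Error, n=300 (n=270) | Two-way bias, points | Error, n=300 (n=270) |
|---|---|---|---|---|
| 50% | 0 | 5.0% (5.0%) | 0 | 5.0% (5.0%) |
| 60% | 0.5 | 5.2% (5.2%) | 1.0 | 5.7% (5.6%) |
| 70% | 1.0 | 5.7% (5.6%) | 2.0 | 7.8% (7.5%) |
| 80% | 1.5 | 6.6% (6.4%) | 3.0 | 11.4% (10.7%) |

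**5. Benefit of 4/6 blocks, same behaviour.** Let q be the share of all patients whose arm is predicted correctly, counting patients with no prediction as 0.5. Acting on half of the predictable patients gives bias = 0.5 × (2q−1) × k × 0.10. For block 2 at g = 0.80, q = 0.5 × (0.5 + 0.8) = 0.65, and the two-way bias is 0.5 × 0.30 × 2 × 0.10 = 3.0 points, which agrees with the table. For undisclosed 4/6 blocks at g = 0.80, by simulation:

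- Best guesser who suspects the 4/6 mix: q about 0.575–0.578, so 1.5–1.6 points two-way. Allowing for variation between simulations, 1.4–1.6 two-way and 0.7–0.8 one-way.
- Simple running tally: q about 0.537 (50 patients per hospital) to 0.569 (10 per hospital), so about 0.7–1.4 points two-way and 0.4–0.7 one-way.

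**The case against.** The strongest reply is that this is a masked trial with matching placebo. Codes are held by the pharmacy, evaluators are blinded, unblinding is meant to be rare, and nothing in the documents shows that arms can be guessed. Settings aims to recruit every possible patient in the first year, and Collaborators' responsibilities asks that all TBI patients be considered promptly; both work against choosing the second of a pair. The doctor enrolling the second patient also need not have seen the first. All of this stands. It lowers the chance that the first arm is learned or used, but does not break the link to the partner, and the recruitment aims do not enforce consecutive enrolment.

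Three stronger readings are tempting, and none is supported.

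- **That half of all allocations are predictable.** This needs every first arm to be known; the documents give no guessing or unblinding rate.
- **That each emergency unblinding in itself unmasks the partner.** It does so only for someone who knows the block size, the pack order and the partner's number. Concealment is affected only if the partner is not yet enrolled. Nothing says that the neuropsychologists who score the GOSE are told an arm.
- **That larger blocks nearly remove the problem.** Bias appears to fall from 3 to 0.4–0.8 points if 4/6 blocks are scored on a random quarter of all patients while block 2 is scored on predictable patients. Scored on a random quarter of all patients, block 2 itself gives only 0.25 × 0.30 × 2 × 0.10 = 1.5 points. On equal terms the best guesser's bias about halves.

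**Conclusion.** The concern holds as a conditional design weakness, worth correcting in lists not yet in use. Confidence is high for the link between partners, given packs used in list order from the start of each hospital's list. That is the natural reading of the text, but still an assumption.

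Confidence in the size is low, because guess accuracy, share acted on and the 10-point steer are all assumed. Under those assumptions the one-way case is modest: at most 1.5 points and 6.6% error at 80% guessing. The 11.4% figure is an upper bound that needs 80% accuracy, action on half of all second patients, and every clinician at every hospital steering the same way. It should not set the priority of this point. With no unblinding and no better-than-chance guessing, the effect is zero.

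The case for change is that the stated purpose, balance over time, is also met by larger varying blocks at little cost, while selection at entry cannot be corrected afterwards.

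**What to change.** For the network hospitals, and for unshipped packs at the two current hospitals (starting after a completed pair), generate permuted blocks of randomly varying size, for example 4 and 6, within hospital. Replace the block-size sentence in Randomization with 'permuted blocks of randomly varying size, stratified by hospital'. Remove the sizes from the protocol and site documents and keep them in a restricted randomization file.

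**Cost.** A protocol change agreed by the Trial Steering Committee (Protocol development), possible notification to the ethics committees and the medicines agency that approved the trial (Trial status), a re-run of the list program, and controlled relabelling of unshipped packs to avoid labelling errors. Stock at sites is small: "A limited number of treatments will be available in each" hospital. The largest within-hospital imbalance rises from 1 to 3 patients. With 600 patients over an assumed 56 uneven hospitals, the 95th percentile of the overall arm difference rises from 10 to 14, an efficiency loss of about (14/600)² = 0.05%. Patients already enrolled since August 2020 gain nothing, and most of the benefit depends on the network opening after the interim analysis.

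**Separate and minor, at no cost.** The lists are stratified by hospital, but no analysis in the Analysis section includes it. Add hospital to the primary comparison (for example Mantel-Haenszel) and to the logistic model, with a rule for pooling small hospitals fixed before unblinding.
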